11. SAFETY

Safety analysis set will be used for safety analyses. Safety will be assessed on the basis of AE reports, clinical laboratory data, ECG parameters, physical examinations, and vital signs.

11.1. EXTENT OF EXPOSURE

Study drug administration and randomization schedule will be documented as per subject listings. Frequency counts of number of subjects who received all doses and descriptive statistics of doses and total cumulative doses by treatment group will be presented.

11.2. TREATMENT COMPLIANCE

Treatment compliance is defined as subjects receiving study drug as planned.

Direct observation of the administration of the study drug by study staff will ensure compliance. The date and time of the start and stop of drug administration and volume infused will be listed.

11.3. ADVERSE EVENTS

All AEs will be coded and grouped into Preferred Terms (PT) by System Organ Class (SOC), using the most recent MedDRA Version. All AEs will be summarized by SOCs and PTs.

By definition, the study only collects treatment-emergent adverse events (TEAEs) so all AEs are TEAEs. The percentage of subjects with specific TEAEs will be summarized for each cohort and part (Part A and Part B and Part C).

All AEs will be listed by treatment, subject, SOC, and PT.

TEAEs will be summarized (number of events, number and % of subjects having experienced at least one event) by treatment, SOC, and PT. TEAEs will be also be summarized by intensity and causality. SAEs will be listed and summarized by causality.

Clinical study report narratives will be prepared for deaths, other serious adverse events, and withdrawals due to adverse events.

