6.3.1. Stopping Rules in an Individual Subject or in a Cohort

For this clinical trial a treatment period is defined as period of time from the beginning of dosing of the first study drug on a given dosing day (ie, Either saline placebo or SEL-110 during Part A of the study and SEL-037 during Part B of the study) to the beginning of the next scheduled dose of study drug, and has a typical duration of 28 days.

For Part C (Cohorts 13, 15, and 17), a treatment period is defined as the period of time from the beginning of dosing of SEL-212 to the beginning of the next scheduled dose of study drug.

Individual

For subjects in Cohorts 1 and 2, any subject who has a weekly serum uric acid value ≥ 6 mg/dl or $>50\%$ of their baseline (where baseline value refers to the pre-dose serum uric acid level from visit 4, Day 0, treatment period 1) at Day 21 of their current treatment cycle will not be eligible for the next dosing of SEL-037. The subject will be followed for 30 days post the last dose of study drug at which time they will have an End of Study assessment and their participation in the study will be terminated.

In Cohorts 3-8, 10-13, 15, and 17 only subjects whose ambient blood samples indicate a serum uric acid (sUA) value less than or equal to 1.0 mg/dL at any of the Day 21 visits will be eligible for the next dosing of SEL-212 (or SEL-037). All other subjects will be followed for 30 ± 2 days post the last dose of study drug at which time all of the End of Study assessments will be completed and their participation in the study will be terminated.

Cohort

If 5 subjects in any of Cohorts 1-5 or 7, or if 10 subjects in any of Cohorts 6, 8, 10, 11, or 12 have met the requirements for individual stopping of their participation in the trial as described above or have been stopped based on Section 6.4 then that cohort will no longer have any additional subjects enrolled in it. Those subjects who have been enrolled will continue until they fulfill the requirements

Study: SEL-212/201 Version: 7.1	Effective Date March 19, 2018
------------------------------------	----------------------------------

for individual stopping or complete the clinical trial treatment periods. If they continue to meet the requirements for continued participation they may continue in Part B of the study.

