12.8.2. Adverse Events

The verbatim AE terms in the CRFs will be coded using the Medical Dictionary for Regulatory Activities (MedDRA). By definition, the study only collects treatment-emergent adverse events (TEAE) so all AEs are TEAEs. The percentage of subjects with specific TEAEs will be summarized for each dose.

All adverse events will be listed sorted by dose, subject, system organ class and preferred term.

TEAEs will be summarized (number of events, number and % of subjects having experienced at least one event) by dose, system organ class and preferred term. TEAEs will be also summarized by intensity, and by causality. SAEs will be only listed. A narrative will be produced for those subjects who have discontinued treatment due to an adverse event or who experienced a Grade 3 or higher events.

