4.3. SAFETY ENDPOINTS

The primary objective of this study is to assess the safety and tolerability of multiple IV infusions of SEL-212. Safety assessments will be based on medical review of adverse event (AE) reports and the results of vital sign measurements, electrocardiograms (ECGs), physical examinations, and clinical laboratory tests. These endpoints will be measured at the time points specified in the protocol in Section 1.1, Schedules of Events. The primary endpoints are frequencies of AEs, serious AEs (SAEs), AEs leading to discontinuation, and ECG and laboratory abnormalities occurring up to 30 days after the last dose of study medication.

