15.2.5.2. Table Conventions

- Units will be included where available
- If the categories of a parameter are ordered, then all categories between the maximum and minimum category should be presented in the table, even if n=0 for all treatment groups in a given category that is between the minimum and maximum level for that parameter. For example, the frequency distribution for symptom severity would appear as:

Severity Rating	N
severe	0

Statistical Analysis Plan

moderate	8
mild	3

Where percentages are presented in these tables, zero percentages will not be presented and so any counts of 0 will be presented as 0 and not as 0 (0%).

- If the categories are not ordered (e.g., Medical History, Reasons for Discontinuation from the Study, etc.), then only those categories for which there is at least 1 subject represented in 1 or more groups should be included.
- An Unknown or Missing category should be added to any parameter for which information is not available for 1 or more subjects.
- Unless otherwise specified, the estimated mean and median for a set of values should be printed out to 1 more significant digit than the original values, and standard deviations should be printed out to 2 more significant digits than the original values. The minimum and maximum should report the same significant digits as the original values. For example, for systolic blood pressure:

N	XX
Mean (SD)	XX.X (XX.XX)
Median (Min, Max)	XX.X(XX.X, XX.X)
95% CI	(XX,XX, XX,XX)

- P-values should be output in the format: “0.xxx”, where xxx is the value rounded to 3 decimal places. Any p-value less than 0.001 will be presented as <0.001. If the p-value should be less than 0.0001 then present as <0.0001. If the p-value is returned as >0.999 then present as >0.999
- Percentage values should be printed to one decimal place, in parentheses with no spaces, one space after the count (e.g., 7 (12.8%), 13 (5.4%)). Pre-determine how to display values that round down to 0.0. A common convention is to display as '<0.1', or as appropriate with additional decimal places. Unless otherwise noted, for all percentages, the number of subjects in the analysis set for the treatment group who have an observation will be the denominator. Percentages after zero counts should not be displayed and percentages equating to 100% should be presented as 100%, without any decimal places.

Statistical Analysis Plan

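### The adverse event tables do not link events to exposure, so differences between cohorts mix risk per dose with the number of doses received

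*SAP*

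**What the plan says.** SAP 4.3 defines the primary endpoints: "The primary endpoints are frequencies of AEs, serious AEs (SAEs), AEs leading to discontinuation, and ECG and laboratory abnormalities occurring up to 30 days", counted from the final dose. For AEs, SAP 11.3 plans that "The percentage of subjects with specific TEAEs will be summarized for each cohort and part", and a table by treatment, system organ class and preferred term giving "number of events, number and % of subjects having experienced at least one event". Protocol 12.8.2 is of the same kind: "The percentage of subjects with specific TEAEs will be summarized for each dose". The default for percentages in SAP 15.2.5.2 is that "the number of subjects in the analysis set for the treatment group who have an observation will be the denominator". A later bullet there notes that the denominator needs thought and points to the number of subjects exposed, not to doses or time.

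SAP 11.1 plans a separate description of doses and cumulative doses by treatment group.

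Exposure is set by Protocol 6.3.1. In Cohorts 1 and 2, "any subject who has a weekly serum uric acid value" of 6 mg/dL or more, or above 50% of baseline, at Day 21 receives no further dose. A different rule governs Cohorts 3-8, 10-13, 15 and 17, where the next dose goes to "only subjects whose ambient blood samples indicate a serum uric acid (sUA) value less than or equal to 1.0 mg/dL", judged on the Day 21 visit. Stopped subjects are followed for about 30 days after their last dose and then leave the study.

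**The concern.** The number of doses is an outcome of treatment, and it sets the time during which an AE can be recorded. Two cohorts with the same risk at each infusion will show different percentages of subjects with an event if one keeps more subjects on treatment. The protocol gives reason to expect unequal continuation: Protocol 4.3.2.3 reports more sustained uric acid control at higher SEL-110 doses, and the continuation threshold itself differs between Cohorts 1-2 and the rest.

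Cohorts will be compared on safety. Protocol 4.5.1 says the Cohort 15 regimen was chosen partly so that its safety could be compared with other Part C regimens. Protocol 6.3 lets AEs and infusion reaction rates within a cohort decide whether that cohort goes on. Protocol 4.4.1 suggests infusion reactions are more common with repeated dosing. If the tables ignore the number of doses, a difference between cohorts could be read as an effect of the SEL-110 dose on safety when part of it is only a difference in exposure.

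Splitting by part does not remove this. Part A still mixes one to three doses, and Part C is a single block of one to five.

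**Working it through.** The documents give no AE rate, continuation rate or power for this endpoint (SAP 3.6 says only that numbers suffice for the objectives), so there is no figure of theirs to reproduce.

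**1. Follow-up.** After one dose: about 30 days. After five doses at 28-day intervals: 4 × 28 + 30 = 142 days.

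**2. Model for a whole cohort.** Let h be the probability of the event at each dose, constant and unrelated to continuation. Let c be the probability of passing each Day 21 gate, and K the maximum number of doses (3 in Part A, 5 overall).

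- P(k doses) = c^(k−1) × (1 − c) for k < K, and c^(K−1) for k = K
- Crude % = Σ P(k) × [1 − (1 − h)^k]
- Mean doses = 1 + c + … + c^(K−1)

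**3. Inputs, all assumptions.** They are anchored where the documents allow:

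- h = 4/31 = 12.9%: headache after single-dose SEL-212, Protocol 4.3.2.3.
- h = 4/20 = 20%: infusion related reaction with SEL-110 alone, Protocol 4.3.2.2.
- h = 5% as a low value.
- c from 0.2 to 0.9, with 17/31 = 0.548 between them. That fraction is subjects with a uric acid effect beyond 30 days (Protocol 10.1.1); it does not apply the 1.0 mg/dL rule.

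**4. Part A with h = 12.9%.** The probability of at least one event is 12.9%, 24.1% and 33.9% after one, two and three doses.

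- c = 0.2: 0.80 × 12.9 + 0.16 × 24.1 + 0.04 × 33.9 = 15.5%
- c = 0.9: 0.10 × 12.9 + 0.09 × 24.1 + 0.81 × 33.9 = 30.9%

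**5. Results.**

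| | c = 0.2 | c = 0.548 | c = 0.9 |
|---|---|---|---|
| Part A (K = 3), h = 12.9% | 15.5% | 22.0% | 30.9% |
| Five doses (K = 5), h = 12.9% | 15.6% | 24.1% | 42.0% |
| Five doses, h = 5% | 6.2% | 10.0% | 18.7% |
| Five doses, h = 20% | 23.8% | 35.1% | 57.6% |
| Mean doses (K = 5) | 1.25 | 2.10 | 4.10 |

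Within a row the risk per dose is identical; only continuation differs. Events per dose do not move: at h = 12.9%, 0.161/1.25 and 0.528/4.10 are both 0.129.

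**6. Direction.** A cohort with 20% risk per dose and c = 0.2 shows 23.8%. Against 12.9% and c = 0.9 (42.0%) the ranking is reversed. Against 5% and c = 0.9 (18.7%) it is preserved. The outcome depends on values the documents do not give.

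**7. Part B denominator.** The share of a cohort reaching dose 4 is c³: 0.8%, 16.5% and 72.9%. In a cohort of 20 with c = 0.548, that is 20 × 0.165 = 3.3 subjects. If three are dosed, one subject with an event is 1/20 = 5% of the cohort or 1/3 = 33% of those dosed. SAP 11.3 does not say which applies.

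**The case against.** The plan provides more than percentages. It counts events, and SAP 11.1 describes doses by treatment group, so a reader could divide one by the other. AEs are listed by subject and infusion times are listed (SAP 11.2). The AE analysis is descriptive, with no test between cohorts, and the primary objective is to assess SEL-212, not to rank cohorts. The proportion of subjects with an event under a regimen together with its stopping rule is a legitimate quantity. All of this stands. What remains is that no planned table joins events to exposure, and n/N by period cannot be recovered from the summary tables.

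Three stronger readings are tempting and not supported:

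- *That a more effective cohort will look less safe.* This needs equal risk per dose. Protocol 4.5 expects anaphylaxis risk to fall as the SEL-110 dose rises, and the looser rule in Cohorts 1-2 may keep those subjects on treatment longer, so the net direction is open.
- *That the gap is 4.7-fold (142/30), or 10% against 41% (1 − 0.9^5) at an assumed 10% risk per dose.* Those figures compare one subject given one dose with one given five. Every cohort mixes dose counts. In tables split by part, five doses fall in one block only in Part C, where the three cohorts share one continuation rule.
- *That the whole primary endpoint is distorted.* Laboratory and ECG data are summarised by scheduled time point (SAP 11.4 and 11.6), so the point concerns the AE tables.

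**Conclusion.** The concern holds for comparisons of AE percentages between cohorts. Under the assumptions above, differing continuation alone can roughly double a Part A percentage (30.9/15.5 = 2.0) and raise a five-dose percentage about 2.7-fold (42.0/15.6) at the same risk per dose. That rests on a constant risk per dose, independence of risk from continuation, and a wide assumed spread in c. If continuation proves similar across cohorts, the effect shrinks accordingly. The absence of any AE table by exposure or period, and the undefined Part B denominator, are matters of record and rest on no assumption. The crude tables are not wrong. They are insufficient for attributing cohort differences to dose.

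**What to change.** Keep the crude tables and add to SAP 11.3:

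- **(a) TEAE n/N by cohort and treatment period**, with N the subjects dosed in that period and events assigned by onset. This also settles the Part B denominator. Period 1 precedes every uric acid gate, so it is the comparison free of response selection, but it answers a single-dose question. Periods 2 to 5 should therefore be shown for the multiple-dose objective, with a note that subjects in them are selected responders.
- **(b) Supportive event rates per dose administered and per subject-month, by cohort**, with a statement that they assume constant risk. Selection of responders into later periods makes that assumption doubtful, so these rates should not stand alone.

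AE onset dates (Protocol 11.2.2) and infusion start and stop times (Protocol 8.3) are already collected, so conduct and data capture do not change. The cost is a few extra tables, with small denominators in later periods.

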11.4. LABORATORY EVALUATIONS

Laboratory data will be summarized by the type of laboratory test. Normal reference

Statistical Analysis Plan

ranges and markedly abnormal results will be used in the summary of laboratory data. Data will be flagged according to the reference limits (High or Low), if applicable. Descriptive statistics will be calculated for each laboratory analyte at baseline and at each scheduled time point for each dose and treatment. Changes from baseline results will be presented descriptively as well as in pre- versus post-treatment cross tabulations (with classes for below, within, and above normal ranges). A listing of subjects with any laboratory results outside the reference ranges will be provided.

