7.2. Subject Exclusion Criteria

1. History of anaphylaxis or severe allergic reactions;
2. History of any allergy to pegylated products, including peginterferon alfa-2a (Pegasys[®]), peginterferon alfa-2b (PegIntron[®]), pegfilgrastim (Neulasta[®]), pegaptanib (Macugen[®]), pegaspargase (Oncaspar[®]), pegademase (Adagen[®]), peg-epoetin beta (Mircera[®]), pegvisomant (Somavert[®]), certolizumab pegol (Cimzia[®]), naloxegol (Movantik[®]), peginesatide (Omontys[®]), pegaptanib (Macugen[®]) and doxorubicin liposome (Doxil[®]);

3. Medications which are known CYP3A4 inhibitors or inducers **MAY** be exclusionary. Patients taking medications that are known CYP3A4 inhibitors or inducers including natural products such as St. John’s Wort or grapefruit juice may be included **ONLY** if they discontinue the medication 14 days before dosing and are able to remain off the medication for the duration of the study.
4. Drugs known to interact with Rapamune such as cyclosporine, diltiazem, erythromycin, ketoconazole (and other antifungals), nifedipine (and other calcium channel blockers), rifampin, verapamil unless they are stopped 2 weeks prior to starting the trial and will not be used during the trial.
5. Women of child bearing potential, Defined as:
 - <6 weeks after surgical bilateral salpingo-oophorectomy with or without hysterectomy
 - Pre or perimenopausal (< less than 24 months of natural amenorrhea)
6. Initiation or change in dose of hormone-replacement therapy for menopausal women less than 1 month prior to the Screening Visit or during the Screening Phase would be exclusionary. If after being on a stable dose of hormone-replacement therapy for one month the patient may be considered for the study if she continues to meet all other inclusion and exclusion criteria
7. Uncontrolled diabetes with baseline HbA1c $\geq 8\%$;
8. Fasting screening glucose greater than 240 mg/dL
9. Fasting triglyceride greater than 300 mg/dl;
10. Fasting LDL cholesterol greater than 200 mg/dl;
11. Glucose-6-phosphate dehydrogenase deficiency;
12. Uncontrolled hypertension: Blood pressure >170/100 at screening and 1 week prior to dosing
13. Individual laboratory values which may be exclusionary
 - White blood cell count less than 3.5×10^9 /L
 - Serum aspartate aminotransferase (AST) or alanine amino transferase greater than 3x upper limit of normal (ULN) in the absence of known active liver disease
 - Glomerular filtration rate less than 40 ml/min/1.73 m²

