19.1.2. Laboratory Data

K. Hematology

	1 (Mild)	2 (Moderate)	3 (Severe)	4 (Life-Threatening)
K1. Hgb (g/dL) decrease from pre-treatment	1.0-1.4	1.5-2.0	2.1-2.9, or Hgb <8.0, >7.0	≥3.0; or Hgb <7.0
K2. Leukopenia (total WCB) X 1000	3.0-3.9	2.0-2.9	1.0-1.9	<1.0
K3. Neutopenia (X 1000)	1.5-1.9	1.0-1.4	0.5-0.9	<0.5
K4. Lymphopenia (X 1000)	1.5-1.9	1.0-1.4	0.5-0.9	<0.5
K5. Platelets (X 1000)	75-LLN	50-74.9	20-49.9; platelet transfusion required	<20; recurrent platelet transfusions

L. Chemistry

	1 (Mild)	2 (Moderate)	3 (Severe)	4 (Life-Threatening)
L1. Hypercalcaemia (mg/dL)	1.1 x ULN-11.5	11.6-12.5	12.6-13.5; or symptoms present	>13.5; or associated coma
L2. Hyperglycemia (mg/dL) (fasting)	140-160	161-250	251-500	>500, or associated with ketoacidosis
L3. Hyperkalaemia (mg/dL)	5.50-5.9	6.0-6.4	6.5-7.0 or any ECG change	>7.0 or any arrhythmia
L4.	-	--	--	--
L5. Hypocalcaemia (mg/dL)	0.9 X LLN-7.8	7.7-7.0	6.9-6.5; or associated with symptoms	6.5 or occurrence of tetany
L6. Hypoglycemia (mg/dL)	55-64 (no symptoms)	40-54 (or symptoms present)	30-39 (symptoms impair function)	<30 or coma
L7. Hyponatraemia (mg/dL)	N/A	125-129	120-124	<120
L8. Hypokalaemia (mg/dL)	N/A	3.0-3.4	2.5-2.9	<2.5
L9. CPK (also if polymyositis)	1.2-1.9 X ULN	2.0-4.0 X ULN	4.0 X ULN with weakness but without life-threatening signs or symptoms	>4.0 X ULN with signs or symptoms of rhabdomyolysis or life-threatening
L10. Serum uric acid	1.2-1.6 X ULN	1.7-2.9 X ULN	3.0-5.0 X ULN or gout	N/A
L11. Creatinine (mg/dL)	1.1-1.3 X ULN	1.3-1.8 X ULN	1.9-3.0 X ULN	>3.0 X ULN
L12. SGOT (AST)	1.2-1.5 X ULN	1.6-3.0 X ULN	3.1-8.0 X ULN	>8.0 X ULN
L13. SGPT (ALT)	1.2-1.5 X ULN	1.6-3.0 X ULN	3.0-8.0 X ULN	>8.0 X ULN
L14. Alkaline phosphatase	1.1-2.0 X ULN	1.6-3.0 X ULN	3.0-5.0 X ULN	>5.0 X ULN
L15. Total bilirubin	1.1-1.4 X ULN	1.5-1.9 X ULN	2.0-3.0 X ULN	>3.0 X ULN
L16. LDH	1.3-2.4 X ULN	2.5-5.0 X ULN	5.1-10 X ULN	>10 X ULN

M. Urinalysis

	1 (Mild)	2 (Moderate)	3 (Severe)	4 (Life-Threatening)
M1. Hematuria	Micro only	Gross, no clots	Clots, transfusion <2 units	Transfusion required
M2. Proteinuria (per 24 h)	300–500 mg (tr/1+)	501–1999 mg (2+)	2-5.0 g (3+) nephrotic syndrome	5.0 g (4+) anasarca
M3. WBC in urine	N/A	N/A	Indicating acute interstitial nephritis	Associated with acute renal failure
M4. Uric acid crystals	Present without symptoms	N/A	With stones or symptoms of stones (e.g. renal colic)	Causing renal outflow obstruction and hospitalization

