6. GENERAL ASPECTS FOR STATISTICAL ANALYSIS

6.1. GENERAL METHODS

SAS® version 9.3 will be used for all statistical analyses and tabulations.

In general, summaries will present data by treatment/cohort and assessment time where appropriate. Unless stated otherwise, descriptive summaries will include n, mean, standard deviation, median, minimum, and maximum for continuous variables, and n and percent for categorical variables. If there are multiple assessments collected on the same scheduled time within the windows, the average of these assessments will be used. For tabulated safety summaries, only the scheduled assessments will be included in the summary tables.

Data collected at unscheduled visits will be included in the data listings but will not be included in the analyses. The data for the EOS visit at day 140 will be separated from the Early Termination visit data and will be summarized for all the subjects within the defined population who reached this visit. An additional observational visit for subjects with <6 mg/dL uric acid concentration on day 140 (approx. 30 days after last dose) were scheduled at approx. 170 days from 1st dose. The data for the observational visit will be reported and summarized for all subjects participating in this visit. Data for Early Termination visits will be listed with actual day from dose included and will not be summarized. The last result for repeat test at screening visit will be considered as final and will be included in summaries. Previous results will be listed but not summarized.

Adverse events and medical history will be coded according to the most recent Medical Dictionary for Regulatory Activities (MedDRA) version. Prior and concomitant medications will be coded using the most recent WHO Drug Dictionary version.

Derivation of PK parameters will be performed using Phoenix WinNonLin 6.4 or higher on a Windows 7 platform or higher.

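### The one defined laboratory frequency in the SAP, a below/within/above-normal shift table, cannot count worsening in subjects who enter already abnormal on values SEL-110 is expected to worsen

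*SAP*

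**What the plan says.** SAP 4.3 states the primary endpoint as counts: "The primary endpoints are frequencies of AEs, serious AEs (SAEs), AEs leading to discontinuation, and ECG and laboratory abnormalities", up to 30 days after the last dose. SAP 11.4 delivers the laboratory part, and Protocol 12.8.3 matches it. It plans four kinds of output:

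- Summaries by visit: "Descriptive statistics will be calculated for each laboratory analyte at baseline and at each scheduled time point for each dose and treatment".
- Change from baseline, shown with descriptive statistics and also through "pre- versus post-treatment cross tabulations (with classes for below, within, and above normal ranges".
- High and Low flags, and use of markedly abnormal results, for which neither document sets limits.
- A listing of subjects with any out-of-range result.

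SAP 6.1 puts the minimum and maximum among the default statistics. It keeps unscheduled values out of the analyses and lists Early Termination data without summarizing them. It adds: "If there are multiple assessments collected on the same scheduled time within the windows, the average of these assessments will be used".

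Protocol 4.4.2 names leukopenia, hyperglycemia, hypertriglyceridemia, hypercholesterolemia and hypophosphatemia among the SEL-110 risks. The exclusions in Protocol 7.2 include "Fasting screening glucose greater than 240 mg/dL", "Fasting triglyceride greater than 300 mg/dl" and LDL above 200 mg/dL. WBC below 3.5 x 10^9/L, AST or ALT above 3 x ULN and phosphate below 2.0 mg/dL are only possible grounds for exclusion. Protocol 19.1.2 carries the graded RCTC v2.0 laboratory scale, with rows such as "K2. Leukopenia (total WCB) X 1000". The scale is used to grade adverse events. No table of laboratory values by grade is planned.

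**The concern.** A primary endpoint stated as a frequency needs a rule that says which subjects count. For laboratory data the only such rule is the three-class table. A subject above normal at baseline can move in that table only by improving or by crossing to the other side of the range; further deterioration leaves the cell unchanged. The entry limits let in subjects who are already outside the normal range on the same analytes that Protocol 4.4.2 expects rapamycin to push further in that direction. The table is therefore least informative in the subjects where metabolic worsening matters most.

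The SAP treats ECG data differently. ECG abnormalities sit in the same primary endpoint, and SAP 11.6 gives QTc tiers for absolute values (>450, >480, >500 ms) and for change from baseline (30 to <60, and 60 or more), although for a listing. Laboratory data have no equivalent tiers.

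**Working it through.** The plan states no figure for this endpoint, so there is nothing to reproduce. The check classifies illustrative pairs of values that eligibility allows, first in the SAP's three classes and then by RCTC grade.

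**Inputs from the documents.** Entry limits are from Protocol 7.2. RCTC fasting glucose grades 1 to 4 are 140-160, 161-250, 251-500 and >500 mg/dL. Leukopenia is 3.0-3.9, 2.0-2.9, 1.0-1.9 and <1.0. ALT grade 2 is 1.6-3.0, grade 3 is 3.0-8.0 and grade 4 is >8.0 x ULN.

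**Assumed.** The documents give no laboratory reference ranges, so they were varied: glucose ULN 99, 110, 125 and 139 mg/dL; WBC LLN 3.5, 4.0 and 4.5; triglyceride ULN 150 and 200 mg/dL; phosphate LLN 2.3, 2.5 and 2.7 mg/dL.

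| Analyte | Baseline to post-dose | Assumed limit | Three-class table | RCTC grade |
|---|---|---|---|---|
| Fasting glucose | 200 to 400 | ULN 99-139 | above to above | 2 to 3 |
| Fasting glucose | 240 to 510 | ULN 99-139 | above to above | 2 to 4 |
| Fasting glucose | 130 to 400 | ULN 99-125 | above to above | 0 to 3 |
| Fasting glucose | 130 to 400 | ULN 139 | within to above | 0 to 3 |
| WBC | 3.6 to 1.5 | LLN 4.0 or 4.5 | below to below | 1 to 3 |
| WBC | 3.6 to 1.5 | LLN 3.5 | within to below | 1 to 3 |
| Triglycerides | 290 to 900 | ULN 150-200 | above to above | no row |
| Phosphate | 2.1 to 1.0 | LLN 2.3-2.7 | below to below | no row |

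The 200 and 240 mg/dL glucose results do not depend on the assumed ULN. The WBC result does: it needs an LLN above 3.6.

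**What the change-from-baseline summary shows.** Let one subject rise by 200 mg/dL while the rest of the cohort is unchanged. The mean change is 200/n: 200/6 = 33.3, 200/10 = 20.0, 200/20 = 10.0. The median is 0 and the maximum is +200 each time. The event is visible in the maximum, but the summary does not say how many subjects worsened.

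**Ungraded analytes on a percent scale.** Triglycerides: (900 - 290)/290 = 210% rise. Phosphate: (2.1 - 1.0)/2.1 = 52% fall. Both would be counted in percent-change bands.

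**Averaging under SAP 6.1.** ALT of 4 and 1.5 x ULN at one scheduled time averages (4 + 1.5)/2 = 2.75 x ULN, turning Grade 3 into Grade 2. This is secondary. It applies only to repeats at the same scheduled time, and ALT is not among the SEL-110 risks in Protocol 4.4.2.

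**The case against.** A reader might infer that laboratory data are presented only in three classes, or that deterioration in these subjects cannot show anywhere. The documents do not support either reading. The same paragraph of SAP 11.4 plans descriptive change from baseline, and with the default statistics that includes the maximum. It also plans a listing of out-of-range results, readable in Part A/B cohorts of 6-20. Protocol 11.2.2.6 makes clinically significant worsening from baseline an adverse event, Protocol 11.2.2.3 grades adverse events on RCTC v2.0, and SAP 11.3 summarizes them by intensity with numbers and percentages. Adverse event frequencies are themselves primary.

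This stands, and it limits the point. It does not remove it. The maximum and the listing are not frequencies. The adverse event route depends on investigator judgment. Markedly abnormal results would supply a count if they had limits, but they have none. Two rules narrow the tables further: unscheduled values are not analysed, and Early Termination values are listed only. The second matters because the serum uric acid stopping rule in Protocol 6.3.1 ends participation early by design.

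Two further objections are fair. How common the problem is cannot be read from the documents, and the HbA1c exclusion at 8% in uncontrolled diabetes reduces the number of hyperglycemic entrants. RCTC also cannot be applied to every row in 19.1.2, so the fix has to be selective.

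**Conclusion.** The point holds in this form: the three-class table cannot count worsening within an already abnormal class, and the SAP defines no other laboratory frequency that would. For fasting glucose of 161-240 mg/dL at entry this follows from the protocol's own scale, for every ULN tested. For WBC, triglycerides and phosphate it rests on assumed reference limits.

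The aggregate size cannot be computed, because the share of subjects abnormal at baseline is not given. As a guide, one uncounted subject is 1/6 = 16.7% of the smallest planned Part A/B cohort and 1/20 = 5% of the largest. No hypothesis test or sample size depends on this endpoint, so the consequence is under-reported severity in the primary safety tables. A better method is available at low cost from a scale already in the protocol, so the change is worth making before database lock.

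**What to change.** In SAP 11.4:

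1. Add, by cohort, a table of baseline RCTC v2.0 grade against worst post-baseline grade for analytes with both an RCTC row and scheduled post-baseline samples: fasting glucose, WBC, neutrophils, lymphocytes, platelets, AST, ALT, bilirubin, creatinine, sodium and potassium. Include alkaline phosphatase once its overlapping grades (1.1-2.0 and 1.6-3.0 x ULN) are resolved. State a rule for shared boundaries, such as ALT at 3.0 and creatinine at 1.3 x ULN.
2. Show hemoglobin as worst RCTC grade of decrease from baseline, since that row is defined mainly by decrease.
3. For triglycerides, total and LDL cholesterol and phosphate, which have no RCTC row, count subjects by pre-specified bands of worst percent change in the adverse direction, for example <25%, 25 to <50%, 50 to <100% and 100% or more, as far as each analyte allows.
4. Use these grades and bands as the definition of markedly abnormal.
5. Derive the worst value from individual results before any averaging under SAP 6.1, and include unscheduled and Early Termination values.

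Leave out CPK and LDH (not in the schedules of Protocol 19.4), calcium and urinalysis (scheduled at screening only), and uric acid (its Grade 3 includes gout, which this population has at entry).

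The cost is SAP wording, some programming and more tables in small cohorts. No new samples are needed.
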